Feb 11th 2017

EPoS
the European Polyp Surveillance trial group

PROTOCOL. Version Feb 11 2017

Amendments:

February 11th 2017

PROTOCOL SUMMARY AND SIGNIFICANCE

This protocol describes the epos (ancient Greek (Επος) for “story”) of a group of related clinical trials aiming at addressing one of the most important unsolved challenges in the prevention of colorectal cancer (one of our major cancer killers); the surveillance of patients with premalignant polyps in the large bowel.

This project is timely because large scale colorectal cancer screening programmes are currently rolled out in most Western countries. These programmes are diagnosing large numbers of individuals with premalignant polyps (adenomas and serrated polyps). This creates both a diagnostic and resource dilemma, because the optimal surveillance strategy for these individuals to reduce future cancer risk is currently unknown.

The EPoS trials will randomize or register more than 27,500 individuals in different European countries to different surveillance colonoscopy intervals to disentangle the most effective and cost-effective surveillance strategy for the population. Subjects will be randomized according to their presenting polyp characteristics

The EPoS I trial randomizes patients with low-risk adenomas into 5 or 10-year surveillance; EPoS II randomizes patients with high-risk adenomas into 3 or 5-yearly surveillance; EPoS III will include patients with serrated polyps in a one-arm study with surveillance after 5 and 10 years. The primary endpoint for all three trials is incidence of colorectal cancer after 10 years of follow-up.

This EPoS trials are the largest in polyp surveillance ever conducted. They address a clinical problem affecting hundreds of thousand individuals in Europe and the US each year, it has a large size, and should thus provide definitive results.

1. BACKGROUND

Colorectal cancer (CRC) is a major global disease burden with more than 1.2 million people diagnosed each year. The mortality rate is high, making colorectal cancer one of the major cancer killers worldwide (1).

To attack this public health problem most Western countries have introduced or are about to introduce population screening programmes for CRC. The primary aim of such programmes is the reduction of CRC incidence and mortality in an average risk population. The predominant screening tools for CRC are fecal occult blood testing (FOBT or FIT), flexible sigmoidoscopy and colonoscopy (2). The latter two have the potential to prevent cancer by removing precursor lesions (adenomas). Colonoscopy is the gold standard for detection for polyps and CRC as it has highest sensitivity. It is the examination of choice after a positive screening test other than colonoscopy, as well as for surveillance of high-risk individuals for CRC, e.g. persons with previous adenomas or cancer, or persons with a hereditary risk for CRC.

Due to the increasing use of screening for CRC, more and more people are diagnosed with adenomas. These individuals are in need for surveillance strategies to prevent future CRC and death from CRC. In order for the screening intervention to be efficient, an optimal surveillance interval is of paramount importance (3). However, today, there is a striking lack of scientific knowledge about the risk magnitude of adenoma patients developing CRC in the future. Therefore, no evidence-based risk stratification algorithm has been established (2,4). No studies have convincingly demonstrated that post-polypectomy surveillance reduces CRC incidence or mortality. Some studies have suggested that surveillance colonoscopy may be effective in reducing the risk of colorectal cancer among patients with adenomas (5,6). Recently, a large, nationwide study in an environment of limited surveillance showed no excess risk of colorectal cancer after adenoma removal for low-risk adenomas but a small excess for high-risk patients (7). Thus, the proper surveillance strategy and interval after adenoma removal is currently unknown.

Consequently, although guidelines on polyp surveillance do exist in Europe and the US, they are (due to the lack of adequate scientific evidence) based on

“expert opinion” and low quality data, and they differ in their recommendations (2,4). In fact, all guidelines specifically emphasise the need for large-scale clinical trials to close the knowledge gap in polyp surveillance (2,4).

Because colonoscopy is an expensive and invasive procedure with a certain risk of adverse events and complications, surveillance colonoscopy should be targeted at those individuals who are most likely to benefit. Also, surveillance colonoscopies should be offered at a frequency required to provide adequate protection against development of cancer yet be cost-effective for providers and caregivers (2). Today, surveillance colonoscopy is one of the main indications for colonoscopy, accounting for more than 20% of all colonoscopies performed in patients older than 55 years in the U.S. (8). In many countries, surveillance colonoscopies are filling colonoscopy lists and large amounts of money are spent without knowing whether this is an effective strategy.

On the basis of adenomas characteristics at screening, patients can be stratified into different risk groups for subsequent development of CRC. Usually, patients are classified into low risk and high risk (some guidelines additionally define an intermediate risk group). The most commonly used characteristics are polyp size and number, as well as histologic type (villous or tubular growth pattern), and grade of dysplasia (low grade or high grade dysplasia) (2,4). The low risk group usually includes people with 1-2 tubular adenomas smaller than 10 mm in diameter; and the high-risk group includes individuals with 3 or more adenomas; or any adenoma larger than 9 mm in diameter, or any adenoma with high grade dysplasia or villous growth pattern.

More recently, a new polyp type, the serrated polyp, has been identified as a risk factor and a precursor for CRC (4). In the past, serrated polyps were considered to have no malignant potential, but recent studies indicate that individuals with serrated polyps are at higher risk for CRC than the average population (4). Due to the lack of proper studies, however, there is great uncertainty on the natural course of serrated polyps, the speed of progression and the quantification of subsequent risk for cancer, and thus surveillance intervals for these patients.

Reflecting this, current surveillance recommendations for all groups differ between guidelines (see table 1) and are mostly classified as of low or very low evidence quality (9).

Table 1: Current guideline recommendations for polyp surveillance

	Low-risk adenoma patients	High-risk adenoma patients	Serrated polyp patients
European Union Guidelines (2)	10 years/none	1-3 years	No recommendation
European Society for Gastrointestinal Endoscopy (10)	10 years	3 years	3 or 10 years
United States Multi-Society Task Force (4)	5 years	3 years	3-5 years

Recommended intervals are arbitrary because of the lack of clinical trials with adequate statistical power and long-term follow-up. Thus, it is possible that longer intervals have the same utility in prevention of CRC, with improved cost-effectiveness.

There are only two high-quality randomized clinical trials comparing different intervals in surveillance colonoscopy (11,12). In the US study (11), after baseline colonoscopy with excision of adenomas, follow-up colonoscopy at 1 and 3 years was compared with one colonoscopy at 3 years. There were no differences in the rate of advanced adenomas between the two groups, concluding that a surveillance interval of 3 years may be recommended. The results of this study are the main basis for recommendation of 3 years intervals after removal of high-risk adenomas. The other study (from Denmark) (12) randomized individuals into multiple comparison groups by adenoma characteristics. The study was too small to uncover clinically significant differences between the groups, although there was a trend of CRC being more common in the 4-year surveillance group compared to a 2-year surveillance group.

However, the confidence intervals were very wide (RR 6.2; 95% CI 1.0-117) and thus the results are not conclusive.

In summary, surveillance recommendations after polyp removal are based on low quality evidence, due to the lack of large-scale clinical trials. The aim of this protocol is to address the optimal surveillance intervals for persons with different risks of CRC based on findings at screening colonoscopy in order to reduce the future risk of CRC. We plan to perform two large multinational randomized trials comparing different surveillance intervals in patients with low-risk and high-risk adenomas, and a registration trial to observe the natural history of serrated polyps.

2. OBJECTIVES

The EPoS trials aim to investigate the optimal time intervals for colonoscopy surveillance of patients with polyps of the large bowel. The EPoS trials constitute two parallel-group randomized controlled trials; **EPoS I**; for patients with low-risk adenomas; **EPoS II**; for patients with high-risk adenomas. **EPoS III** is an observational study focusing on serrated polyps.

3. TRIAL ENDPOINTS

3.1 PRIMARY ENDPOINT

The primary endpoint in EPoS I, II and III is CRC incidence. CRC incidence will be compared in the different arms in EPoS I and II, and in EPoS III.

3.2 SECONDARY ENDPOINTS

The following endpoints will also be compared in the different arms in EPoS I and II, and in EPoS III

- Colorectal cancer mortality
- Cost-effectiveness
- Yield of advanced adenomas, adenomas and serrated polyps
- Adverse events within 30 days of colonoscopy (defined as bleeding requiring transfusion or hospitalization, perforation, death or other colonoscopy-related events)
- Differences regarding indication of baseline colonoscopy

3.3 PREDEFINED SUBGROUP ANALYSES

Subgroups defined by variables which may be associated with the risk of CRC and adenoma yield during follow-up will be analysed. These include: patient age and gender, reason for first colonoscopy (colonoscopy screening; colonoscopy after a positive screening test (FIT, FOBT, sigmoidoscopy); clinical symptoms; other indications) and the following polyp characteristics: type of polyp, size of polyp, in case of adenoma: growth pattern (tubular, tubulovillous or villous), grade of dysplasia (high vs. low); multiplicity and location of polyps (proximal vs distal colon).

4. METHODS

4.1 JOINT DESIGN SETTING

EPoS I and II are randomised controlled trials without drugs. EPoS III is a one-arm observational study. Eligible for all trials are individuals with no history of CRC or adenomas between 40 and 74 years who have undergone colonoscopy with removal of one or more adenomas or serrated polyps at one of the study centres (hospitals in the participating countries, approved for trial participation). The indication for colonoscopy is not restricted in any way, and includes screening as well as clinical symptoms or other indications. At the baseline colonoscopy and before study entry, all polyps have to be completely removed, the colon fully investigated with adequate quality of bowel preparation, and the colonoscopy needs to be performed under high quality standards.

~~Patients can be included at any point in time between the baseline colonoscopy and the date of first surveillance colonoscopy.~~

4.1.1 Surveillance colonoscopies

Surveillance colonoscopy is the intervention tool used in all trials. At surveillance colonoscopy, all detected polyps will be registered and described, removed whenever possible and subjected to histopathology. Standard video-colonoscopes are used for the examinations. All required data from endoscopy reports, quality-data used for quality monitoring and histopathologic results must be registered in the central study database. Local pathology labs will serve the participating centres and perform

histopathological analysis of the tissue samples. All histopathology reporting follows WHO guidelines for classification and grading (13). Serrated polyp classifications are according to recent guidelines (13).

4.1.2. Time of surveillance colonoscopies

Surveillance colonoscopies are scheduled at the participating centres according to the time slots defined in the protocol for the different study groups and arms (see below). For all participating patients, a reminder will be sent by the EPOS database management team to the national coordinators and the study-administration of the participating centres approx. 4-6 months before the surveillance colonoscopy is scheduled.

Surveillance colonoscopies are to be performed within a 6-month time interval from the protocol-defined date. Surveillance colonoscopies which are performed earlier than 6 months before or later than 6 months after the protocol-defined date are recorded as a protocol deviation (but results as well as reason for deviation are to be recorded in the trial database).

4.2 JOINT INCLUSION CRITERIA FOR ALL EPOS TRIALS AT BASELINE COLONOSCOPY

[figure not shown]
- * Men and women age 40-74 years
- * Cecal intubation (preferably documented by images/video of the appendiceal orifice and the ileocecal valve; but not required).
- * Adequate colonic cleansing, with Boston Bowel Cleansing Score equal or higher than 2 points in all colonic segments.
- * Complete excision of all polyps at baseline colonoscopy findings (as judged by the trial endoscopists)
- * Randomisation must be performed no longer than 26 weeks (182 days) from completion date of baseline colonoscopy

4.3 JOINT EXCLUSION CRITERIA FOR ALL EPOS TRIALS

- Lack of consent
- History of CRC or adenomas
- More than 10 adenomas

- History of serrated polyps \geq 10 mm in diameter at any colorectal location or \geq 5 mm if located proximal to the splenic flexure
- Serrated polyposis syndrome (SPS) defines as:
 - \geq 20 serrated polyps, or
 - At least 5 serrated polyps proximal to the sigmoid colon, of which at least two are $>$ 10 mm in size, or
 - Any serrated polyp proximal to the sigmoid colon in a first degree relative with SPS.
- Incomplete colonoscopy
- Incomplete endoscopic excision of polyps (exception: In consistence with current guidelines (2, 4, 10), small (1-4 mm in diameter), whitish polyps in the rectum are considered insignificant for future colorectal cancer risk and are therefore not included in evaluation of patients for the EPoS trials)
- Non retrieval of any polyp (for EPoS I) or non retrieval of any polyp $>$ 9 mm and the patient could be consistently classified as high-risk (for EPoS II)
- Genetic cancer syndrome (adenomatous or serrated polyposis syndrome; Lynch or Lynch-like syndrome)
- Inflammatory bowel disease
- History of surgical colon resection for any reason
- Severe co-morbidity with reduced life expectancy (NYHA 3-4)
- On-going cytotoxic treatment or radiotherapy for malignant disease
- Long-lasting attention and nursing services (somatic or psychosocial, mental retardation).

Figure 1: EPOS trials overview

4.3 SPECIFIC DESIGNS AND SETTINGS

4.3.1. EPoS I

Eligible individuals are persons with low-risk adenomas removed at baseline colonoscopy (1-2 tubular adenomas size <10mm with low-grade dysplasia) and no serrated polyps with dysplasia, with diameter 10 mm or larger at any location or with diameter 5 mm or larger proximal to the splenic flexure.

Individuals will be **randomized** into one of two intervention groups:

Group 1: Surveillance colonoscopy at 5 and 10 years after baseline colonoscopy.

Group 2: Surveillance colonoscopy at 10 years after baseline colonoscopy.

The primary and secondary endpoints will be analyzed directly after the 10 year surveillance colonoscopy, (figure 1).

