4.3.2 EPoS II

Eligible individuals are persons with high-risk adenomas removed at baseline colonoscopy (three to ten adenomas; or one or more adenoma w/size \geq 10mm, or one or more adenoma with high-grade dysplasia or villous growth pattern).

Individuals will be **randomized** into one of two intervention groups:

Group 1: Surveillance colonoscopy 3 and 5 years after baseline colonoscopy

Group 2: Surveillance colonoscopy 5 years after baseline colonoscopy

Feb 11th 2017

Individuals in both group 1 and group 2 will be subjected to a final colonoscopy surveillance after 10 years (figure 1).

The primary and secondary endpoints will be analysed directly after the 10 year surveillance colonoscopy, (figure 1). A secondary analysis will be performed after the 5 year colonoscopy.

For centers with current guidelines for 1 year surveillance for multiple or large (>20mm) adenomas; they may exclude those patients.

In both EPoS I and EPoS II, surveillance intervals after the first surveillance colonoscopy take into account findings at the first surveillance colonoscopy. Surveillance intervals after first surveillance colonoscopy are shown in **Figure 2A (EPoS I) and-B (EPoS II)**.

Figure 2. Surveillance intervals after first follow-up colonoscopy in EPoS I and II

Figure 2A: EPoS I

[figure not shown]
[figure not shown]

Figure 2B; EPoS II

LRA: Low risk adenoma; HRA: High-risk adenoma

Figure 2C: Polyp characteristics and eligibility in EPoS. SP: Serrated polyp, TSA: Traditional Serrated Adenoma.

Serrated polyp	≥10mm SP and/or SSA with dysplasia and/or TSA	≥5mm SP in the proximal colon	<10mm SP with no dysplasia in the distal colon	<5mm SP with no dysplasia in the proximal colon	None
No adenoma	EPoS III	EPoS III	No inclusion	No inclusion	No inclusion
1-2 tubular adenoma <10mm with low-grade dysplasia	EPoS III	EPoS III	EPoS I	EPoS I	EPoS I
>2 adenoma	EPoS II	EPoS II	EPoS II	EPoS II	EPoS II
Villous histology	EPoS II	EPoS II	EPoS II	EPoS II	EPoS II
High grade dysplasia	EPoS II	EPoS II	EPoS II	EPoS II	EPoS II
Adenoma ≥10mm	EPoS II	EPoS II	EPoS II	EPoS II	EPoS II

4.3.3. EPoS III;

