11. STATISTICAL ANALYSIS PLAN

Participants are followed for the primary endpoint (incidence of CRC), until death/incidence of CRC or end of follow-up, whichever happens first. All randomised participants are followed up through national or regional registries, regardless of whether they continue in the study or not. The primary analytic approach of the trial will follow the intention-to-treat (ITT) principle. We will compare the ~~average rate~~

~~of differences for~~ each endpoint between the intervention groups by calculating risk differences and log-rank test ~~fitting a Cox proportional hazards model~~. The limit for the statistical significance will be established in 0.05 and 95% confidence intervals will be calculated. If the distribution of any baseline characteristics is found to be imbalanced between the arms, we will conduct a sensitivity analysis in which those characteristics will be included as covariates in the model.

We will also do analyses to estimate the causal effect that would have been observed if all individuals in the intervention arms had been compliant. We will refer to these analyses as “adherence-adjusted” analyses. We will use two different analytic approaches to obtain “adherence-adjusted” estimates: instrumental variables methods and inverse probability weighting. For comparability, we will translate the estimates from both approaches into a common metric: adjusted (CRC-free) survival curves. To implement instrumental variables methods (with the indicator for treatment arm as the instrument), we will use g-estimation of nested structural models. To implement inverse probability weighted estimation, we will estimate the weights and the parameters of a marginal structural Cox model. The estimation of inverse probability weights in one intervention arm requires the measurement of variables that jointly predict compliance with the baseline intervention and the endpoint. These variables include age, sex, baseline findings, physical activity, family history of colorectal cancer, smoking status, use of aspirin, NSAIDs, and hormone replacement therapy (9).

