12. PILOT PROJECT - COST-EFFECTIVENESS

We have performed a Markov model to compare differential cost of surveillance for advanced adenomas at 3 vs at 5 years ([name], unpublished data). Considering 15 years surveillance, the cost of a 3-year surveillance interval after high-risk adenoma removal would be 602.82 € per patient, whereas the cost with a 5-year surveillance interval would be 548.99 € per patient. That supposes a differential cost of 53.83 € per patient. In Europe, approximately 6.000.000 colonoscopies are performed every year, and in approximately 5% of them high-risk adenomas are diagnosed. Thus, the estimated cost saving of 53.83€ per patient would translate to a total saving of 16.149.000 € per year in Europe. Moreover, a reduction in the number of colonoscopies performed for polyp surveillance will also avoid possible complications for patients. The colonoscopy burden that is currently being used for performing surveillance colonoscopy could be more appropriately used for CRC screening.

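### In EPoS I, colorectal cancer (CRC) mortality is analysed directly after the year-10 colonoscopy, which is the longer-interval arm's first surveillance examination, so the comparison understates any later excess of CRC deaths in that arm

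*Protocol*

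**What the plan says.** Section 3.2 of the protocol lists "Colorectal cancer mortality" and "Cost-effectiveness" among the secondary endpoints to be compared between arms. No time horizon is attached to either.

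Section 4.3.1 gives the EPoS I schedules as "Group 1: Surveillance colonoscopy at 5 and 10 years after baseline colonoscopy" and "Group 2: Surveillance colonoscopy at 10 years after baseline colonoscopy". It then sets one analysis time for everything: "The primary and secondary endpoints will be analyzed directly after the 10 year surveillance colonoscopy". Section 4.3.2 says the same for EPoS II ("The primary and secondary endpoints will be analysed directly after the 10 year surveillance colonoscopy") and adds a secondary analysis after year 5. In EPoS II both arms are examined at years 5 and 10, and the scheduled difference is the year-3 examination.

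Section 13 plans publications after 5 and 10 years and none later. Section 11 (Statistical Analysis Plan) states that "All randomised participants are followed up through national or regional registries", whether or not they stay in the study, but does not say when that follow-up ends. The pilot economic model in section 12 covers high-risk adenomas over a longer period: "Considering 15 years surveillance, the cost of a 3-year surveillance interval after high-risk adenoma removal would be 602.82 € per patient".

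**The concern.** A cut at year 10 suits CRC incidence, polyp yield and 30-day adverse events, which are known at or soon after the examination. CRC death follows diagnosis by months or years.

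In EPoS I the arms follow the same schedule until year 5. The shorter-interval arm is then examined at year 5, and cancers found there have about 5 years in which a death can be recorded. The longer-interval arm is first examined at year 10, at the point where the analysis closes. Screen-detected cancers in that arm enter the incidence count but can hardly enter the mortality count. The truncation is therefore unequal, and it favours the longer interval, which is the experimental arm of a non-inferiority trial.

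Section 11.1 justifies the trial partly by arguing that any survival benefit of more intense surveillance is small in absolute terms. CRC mortality is the endpoint that speaks to that argument, so a small 10-year difference could be given more weight than it can bear.

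**Working it through.** **1. The plan's own figures.** No number is given for mortality or cost-effectiveness, so the only figures to reproduce are the group sizes for CRC incidence. With equal true risks, one-sided alpha 0.05 and 90% power, n = (1.645 + 1.282)² × 2p(1 − p) / margin². For EPoS I (p = 0.01, margin 0.005) this gives 6,783 per arm. The same formula gives 6,852 for EPoS II, and 4,897 and 4,947 at 80% power. All four agree with Table 2. This point does not affect the sample size.

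**2. A simple model for EPoS I.** The first two inputs rest on protocol figures; the rest are assumptions, because the protocol gives none of them.
- Excess cancers in the longer arm equal to the margin: 6,783 × 0.005 ≈ 34.
- This excess is diagnosed in years 5-10, since the schedules are identical until year 5.
- A share s of it is found at the year-10 examination; the rest is diagnosed evenly over years 5-10.
- Five-year case fatality is f, with constant hazard h, so 5h = −ln(1 − f).

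For cancers diagnosed evenly over years 5-10, the mean probability of CRC death is:
- by year 10: 1 − f/(5h)
- by year 15: 1 − [(1 − f) − (1 − f)²]/(5h)

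For cancers found at year 10 it is 0 by year 10 and f by year 15.

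At f = 0.35, 5h = 0.431. The evenly diagnosed cancers have 0.188 by year 10 and 0.472 by year 15. With s = 0.5 (17 cancers of each kind):
- excess deaths by year 10: 17 × 0.188 = 3.2
- excess deaths by year 15: 17 × 0.472 + 17 × 0.35 = 14.0
- visible at year 10: 3.2 / 14.0 = 23%

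Share visible at year 10 over the assumed ranges:

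| 5-year fatality | s = 30% | s = 50% | s = 70% |
|---|---|---|---|
| 20% | 28% | 22% | 14% |
| 35% | 30% | 23% | 15% |
| 50% | 33% | 24% | 15% |

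**3. How much comes from the year-10 examination itself.** In the central case 14.0 − 3.2 = 10.8 deaths fall after the cut. Examination-detected cancers supply 17 × 0.35 ≈ 6.0. The other 17 × (0.472 − 0.188) ≈ 4.8, about 45%, are interval cancers that simply need longer follow-up.

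**4. A second model covering both trials.** A simulation of onset, detection, precursor removal and death was run with its own assumptions: sojourn 2-4 years; precursor removal protecting for 2-4 years; sensitivity 95% for cancer and 80% for precursors; annual CRC death hazard 0.09 after clinical and 0.03 after examination diagnosis; onset risk over 10 years 2% (EPoS I) and 4% (EPoS II). Cancers diagnosed by year 10 are followed to year 15.

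| | EPoS I | EPoS II |
|---|---|---|
| Found at year-10 examination, shorter arm | 13-30 | 25-59 |
| Found at year-10 examination, longer arm | 26-47 | 26-60 |
| Excess CRC deaths by year 10 | 3-8 | 12-18 |
| Excess CRC deaths by year 15 | 13-22 | 21-30 |
| Death ratio by year 10 | 1.17-1.31 | 1.41-1.54 |
| Death ratio by year 15 | 1.31-1.53 | 1.35-1.54 |

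Its EPoS I incidence (91-113 cancers in the shorter arm) is above the plan's 1% (about 68), so only the pattern should be read from it. In EPoS I the ratio rises with follow-up. In EPoS II the year-10 findings are nearly balanced and the ratio hardly moves.

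**5. What a 15-year comparison could show.** Take f = 0.35 and 68 control cancers spread evenly over ten years. The mean probability of CRC death by year 15 is 1 − (0.65 − 0.65³)/(2 × 0.431) = 0.564, or about 38 deaths. Adding the 14 excess deaths gives about 52. The difference divided by its standard error is 14/√(38 + 52) ≈ 1.5, which is roughly 30% two-sided power.

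**The case against.** Several stronger readings are tempting, and the protocol does not support them.

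- **That both trials are biased.** The two sections share the same wording, but in EPoS II both arms are examined at years 5 and 10. Mortality there is immature, not clearly distorted between arms.
- **That the 10-year mortality result is invalid or bound to show no difference.** CRC death by year 10 is a legitimate risk, and some excess is visible by then under every assumption tried. The non-inferiority margins apply to CRC incidence only; no text plans a non-inferiority or no-difference conclusion on mortality.
- **That cost-effectiveness favours the longer interval by construction.** That follows only if costs and life-years are confined to the ten observed years. The protocol states when endpoints are analysed, not the economic horizon, and a model run at year 10 can extrapolate. The 15-year pilot compares 3 with 5 years after high-risk adenomas, which is the EPoS II question, so it does not show that the EPoS I horizon is too short.
- **That cancers found at year 10 have no follow-up at all.** Recruitment takes 2 to 3 years or longer, so a common calendar cut-off could give early entrants some. The wording does not provide for this.

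It is also fair to object that every driving input is assumed and that the simple model gives examination-detected cancers the same fatality as the others. The second model gives them a lower hazard and still places most of the EPoS I excess after year 10. The direction stands; the size is illustrative.

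**Conclusion.** The point holds for CRC mortality in EPoS I. The protocol fixes the mortality analysis at an examination that is one arm's first surveillance, with no later analysis planned, and the resulting truncation favours the longer interval. With case fatality of 20-50% and 30-70% of the excess cancers found at that examination, 14-33% of the excess deaths present by year 15 would be visible at year 10. In the central case a little under half of the shortfall is ordinary immaturity of interval cancers.

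The estimate assumes an excess equal to the 0.5% margin, all of it diagnosed in years 5-10, and a constant death hazard. CRC incidence as the primary endpoint is not touched. This is a worthwhile, inexpensive improvement to a secondary endpoint.

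**What to change.** Keep CRC incidence, yield and adverse events at 10 years. In section 4.3.1, label the 10-year CRC mortality result as interim and descriptive, and add a later registry-based mortality analysis, for example 15 years after baseline. Report it as an estimate with a 95% confidence interval and not as a confirmatory test, given power of only about 30% under the inputs above. Add the later date to section 13. The same addition to section 4.3.2 is optional, for maturity.

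For cost-effectiveness in EPoS I, state that the conclusion will not rest on costs accrued by year 10 alone, and extrapolate beyond year 10 with a model fed by trial incidence and stage.

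The cost is one further registry linkage, a model run, and a final mortality result about 5 years later. No visits or participants are added. The sponsor must confirm that registry follow-up and consent extend that far, since the protocol does not state when follow-up ends.
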